### **Research Design and Methods**

Death by suicide after psychiatric hospitalization is a notable concern in the Veteran population. Although the VA has implemented many strategies to prevent suicide in the post-discharge period, suicide remains an ongoing concern in this population. Based on my preliminary work and available evidence, an intervention that I developed, called PEACE, may be an effective strategy to mitigate suicide risk in Veterans after psychiatric hospitalization because it addresses two key risk factors for suicide after psychiatric hospitalization: lack of social connectedness and poor engagement in care. My central hypothesis is that PEACE reduces suicide risk in Veterans in the period following psychiatric hospitalization by decreasing suicidal ideation. I also hypothesize that PEACE exerts its anti-suicidal effect by improving social connectedness and engagement in care after psychiatric hospitalization. I will conduct an exploratory aim evaluating the number of suicide attempts occurring after discharge. In this CSR&D CDA proposal, I intend to address these hypotheses by testing PEACE under randomized conditions in psychiatrically hospitalized patients. I expect that my work will result in the publication of important papers and will provide me with necessary data to support my goal of becoming an independent clinical researcher who develops, tests, and improves interventions to prevent suicide in Veterans.

### **Overview of Intervention and RCT Design:**

As shown below in **Figure 2**, to test the aforementioned hypotheses, we propose to conduct a single-site, assessor-blinded RCT at the WRJ VAMC comparing PEACE plus standard psychiatric hospital discharge care to standard psychiatric hospital discharge care alone. The trial will enroll patients 18 years and older who are being discharged from the WRJ VAMC inpatient mental health unit (called Ground East, GE). The primary aim is to determine whether PEACE reduces suicidal ideation at one, three, and six months after psychiatric hospitalization. The secondary aim is to determine the mechanism by which PEACE exerts its anti-suicidal effect after hospitalization. An exploratory aim includes describing the number of suicide attempts after discharge.

**Baseline Assessment and Randomization:** Prior to the start of study enrollment, allocation cards will be prepared using a fixed-block randomization scheme. These cards will be put into sealed, opaque, numbered envelopes. The box of envelopes will be stored in a locked cabinet in the study coordinator's locked office.

The study team member will meet with each eligible patient in a private room on GE at the WRJ VAMC around the time of discharge. The study team member will obtain informed consent from the patient and then administer the baseline assessments, which are described under the outcome measures (see below). The baseline visit will take approximately 90 minutes to complete. Study staff will also contact the support person the patient selected to obtain consent from this person.

After obtaining consent and completing the baseline assessments, the study coordinator will take the next numbered envelope from the box (described above) and open the envelope to determine the patient's assignment. In the event that the patient has been assigned to the intervention, the study coordinator will notify the intervention staff in order that the intervention staff can initiate the intervention. Otherwise, the patient will be informed that they have been assigned to usual care.

**PEACE Intervention Description:** Patients assigned to the intervention arm will receive PEACE (please see PEACE manual). The intervention can be delivered by a trained mental health staff member, such as a psychologist, mental health nurse, social worker, or psychiatrist. For simplicity sake, we will use the term "study therapist" to refer to the intervention staff member throughout the rest of this proposal and the accompanying documents.

[figure not shown]
PEACE targets the needs of patients who are being discharged from a VA inpatient mental health unit after having been admitted because of acute suicide risk. Because PEACE is designed to enhance the standard hospital discharge care that patients receive as part of psychiatric hospitalization, patients assigned to PEACE will

continue to have access to standard discharge care (described below). There are no restrictions on the types of treatments that patients may pursue after discharge; however, we will track the treatments that patients decide to utilize after discharge. By comparing PEACE with standard discharge care (including care provided through the Suicide Prevention Coordinator program), we hope to determine whether PEACE enhances standard discharge care. As described below, we conceptualize that the PEACE intervention consists of three synergist components that work to support the patient after discharge:

- Brief Educational Component: Patients receive a one-hour, one-on-one, personalized, brief educational intervention on suicide prevention. The session is performed by the study therapist and takes place on the inpatient mental health unit around the time of discharge. We anticipate that, in most cases, the patients will receive the intervention the day prior to discharge. The education is designed to meet the information needs of Veterans receiving mental health care in the VA and to address barriers to follow-up. The education includes a discussion of the patient's safety plan, draws upon MI techniques, and emphasizes self-efficacy. The sessions are highly interactive, allowing time for questions and providing patients with written materials that they can keep for future reference.

- Seven Regular Contacts after Discharge Component: The patients will maintain regular contact with the same study therapist for seven follow-up contacts (totaling 8 contacts including the initial Brief Educational

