### **Study Population and Recruitment**

The study will be conducted at the WRJ VAMC and will recruit patients hospitalized on Ground East (GE), the facility's 12-bed inpatient mental health unit. GE staff includes psychiatrists, a therapist, nursing staff, a social worker, and trainees from these disciplines. Study staff will attend daily inpatient treatment team meetings in order to identify potentially eligible patients who can be approached about study participation. The inpatient team and attending psychiatrist will make the determination as to when and whether it is clinically appropriate for study staff to approach potentially eligible patients. After approaching eligible patients, study staff will make them aware of the study and determine if they are interested in participating in the study. If patients are interested in the study, study staff will obtain informed consent using a written informed consent document prior to enrolling the patient into the study. During the course of the study, it will be impossible to blind the study therapist or patients to treatment allocation; however, the outcome assessor will remain blind to study assignment throughout the trial. Patients will be instructed during the course of the trial not to reveal their study assignment to the outcome assessor. In order to assist with study retention, reminder letters will be sent in the form of U.S. mail or a phone call, depending on patient preference.

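### One fixed-block sequence at a single site, with no statement that block size is withheld or that recruiters are kept from past assignments, leaves selection bias possible

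*Combined protocol and SAP*

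**What the plan says.** Under Overview of Intervention and RCT Design (Baseline Assessment and Randomization), "allocation cards will be prepared using a fixed-block randomization scheme". On concealment: "These cards will be put into sealed, opaque, numbered envelopes", and "The box of envelopes will be stored in a locked cabinet in the study coordinator's locked office". On operation: "the study coordinator will take the next numbered envelope from the box (described above) and open the envelope to determine the patient's assignment". This step comes only once the patient has consented and the baseline is complete. The coordinator then alerts the intervention staff if the patient is in the PEACE arm. The text gives no block size, does not say who prepares the cards, and describes no varying block sizes, strata or off-site allocation.

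Study Population and Recruitment states that "it will be impossible to blind the study therapist or patients to treatment allocation", while the outcome assessor stays blinded. It also states: "Study staff will attend daily inpatient treatment team meetings in order to identify potentially eligible patients". The roles of these staff are not named. The same paragraph leaves to the inpatient team and attending psychiatrist when and whether a patient may be approached, and Protection Against Risk accepts referrals only from that team.

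The baseline role is described in two ways. The randomization paragraph gives consent and baseline to an unspecified study team member; Study Design gives the baseline assessment to the blinded independent assessor.

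**The concern.** An opaque envelope hides the next card. It does not hide what can be worked out from the cards already opened. With 1:1 blocks of constant size in one unstratified sequence, once one arm's places in a block are used up, the rest of that block is known. The coordinator opens every envelope and so holds the full history.

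Opening the envelope after consent and baseline stops a person from reading the card early. It does not act on the earlier step, when staff decide which patient to approach and on which day. If someone with foreknowledge influences that step, the arms can differ in prognosis before treatment starts, and blinding the assessor later does not undo it.

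**Working it through.** **Inputs.** From Sample Size: 40 per arm evaluable, 46 per arm (92) recruited, design effect 0.5 SD, correlation 0.5, four time points, 80% power, 5% significance. Equal arms imply 1:1 allocation. Block size is not given, so sizes 2 to 8 are assumed and shown as a range.

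**The plan's own figure.** There is no predictability figure to reproduce. The sample size is recovered, taking the test as two-sided: n per arm = 2 × (1.96 + 0.842)² × [1 + 3 × 0.5] / (4 × 0.5²) = 39.24, so 40. Dividing by 0.9 gives 45 against the stated 46. The count of 92 is used below.

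**Certain assignments.** For a block of size b = 2k, with k places per arm, the expected share already fixed by earlier assignments is 1/(k + 1). **Best guess.** Always guessing the arm that is behind gives k + 4^k / [2 × C(2k, k)] − ½ correct guesses per block. For b = 4: 2 + 16/12 − 0.5 = 2.833, and 2.833/4 = 71%. Enumerating all balanced blocks gives the same values:

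| Fixed block size | Known with certainty | Of 92 | Guessed correctly |
|---|---|---|---|
| 2 | 50% | 46 | 75% |
| 4 | 33% | 31 | 71% |
| 6 | 25% | 23 | 68% |
| 8 | 20% | 18 | 67% |

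The two measures need different knowledge. Certainty needs the block size and all past assignments. The best guess needs only the running difference between arms, because every completed block contributes zero to it.

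**Randomly varying blocks.** Simulated for 92 patients, with an observer who has the full history and knows the possible sizes but not their order:

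| Sizes | Known with certainty | Of 92 | Guessed correctly |
|---|---|---|---|
| Fixed 4 | 33% | 31 | 71% |
| 2, 4, 6 | 4% | 4 | 70% |
| 4, 6 | 6% | 5 | 69% |
| 4, 6, 8 | 2.5% | 2 | 68% |

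Varying the size removes most of the certainty but little of the guessing advantage. A mix that includes size 2 is guessed slightly more often than fixed blocks of 6 or 8.

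**Illustration of bias, not an estimate.** Suppose staff steer only when certain, and each steered patient's prognosis shifts by e SD. The expected spurious difference is 2 × e × (certain share). With e assumed at 0.25 to 0.5:
- Size 4: 2 × 0.25 × 0.333 = 0.17 to 2 × 0.5 × 0.333 = 0.33 SD. Simulated two-sided t-tests with no true effect reject in about 12% to 33% of trials.
- Size 6: 0.13 to 0.25 SD, with rejection in about 8% to 20%.

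These compare with a design effect of 0.5 SD. They use a simple t-test, not the planned hurdle model.

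**The case against.** The case against is substantial. The inpatient team controls referral and approach, and the main eligibility criterion rests on the unit psychiatrist. Allocation follows consent and a completed baseline, and Study Design gives that baseline to a blinded assessor. Timing is tied to discharge. Resources Available foresees up to 160 enrolled over four years, 160/48 = 3.3 a month, so there is seldom a queue to reorder. Baseline BSS is collected, and Statistical Analyses plans adjustment for baseline differences.

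Most of this stands as a limit on the risk, not as its removal. Within what the inpatient team allows, unspecified study staff still identify and approach patients. The inpatient team can itself learn assignments, since the first PEACE session takes place on the unit and intervention notes enter the chart. The adjustment is triggered only by P < 0.05. With 46 per arm the standard error of a standardized difference is √(2/46) = 0.21, so true imbalances of 0.17, 0.25 and 0.34 SD would be flagged only about 13%, 22% and 36% of the time. The listed variables do not name baseline BSS, and selection on motivation might not be measured at all.

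A reader might go further and infer that the trial is simply unblinded, that the therapist knows every past assignment, or that staff can in fact predict the next one. The documents do not support these. Assessors are blinded. The therapist is documented as being told only of assignments to PEACE, not of control assignments or of where a block begins. No text shows that anyone who recruits knows the block size.

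**Conclusion.** The point holds as a conditional weakness of the allocation method. The plan fixes the block size, does not say it is concealed, and does not separate knowledge of past assignments from the choice of whom to approach and when. If the size is known or inferred, 20% to 50% of assignments are certain in advance to someone with the full history, for sizes 8 down to 2.

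That range assumes 1:1 blocks in one sequence and an observer who has seen every assignment, which the documents establish only for the coordinator. It measures exposure, not bias. A conclusion that the arms will be unbalanced, or by how much, would not be supported: block size, who recruits and any steering are all undocumented, and the safeguards above limit the route. The change is worth making because it is specific and cheap.

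**What to change.** 1. Generate the allocation list, or its unused remainder, with randomly varying block sizes, preferably without size 2 (for example 4, 6 and 8), and re-issue the unopened envelopes from it.
2. Withhold the sizes and their order from all site staff who approach, consent, treat or assess patients, and say so in the protocol.
3. State that staff who know past assignments, including the coordinator and the therapist, do not choose whom to approach or when. Existing staff can cover this. It is needed because varying blocks alone leave the best-guess rate at about 68%.
4. Reconcile the two descriptions of who takes consent and performs the baseline assessment.

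**Cost.** Re-printing the unused cards, a minor amendment, and a possible final imbalance of a few patients: at most 4 from an unfinished block of 8, plus any imbalance standing if a block is abandoned at the switch. No new staff.

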**Figure 2. Flow chart of study procedures**

d=days; IC = inclusion criteria; m= months; MH = inpatient mental health; w = weeks

visit) over the course of the three months after psychiatric hospitalization. At each of these contacts, the study therapist will monitor the patient's symptoms, assess treatment adherence, review the safety plan with the patient, and, if necessary, assist the patient with engaging in care. The contacts will include the use of MI techniques. The contact sessions are systematic and structured. The contacts are designed to be highly interactive, allowing times for questions and providing patients with written materials that they can keep for future reference. Depending on the patient's preference, the contacts will be delivered via phone, VA Video Connect, or in-person in a private office on the grounds of the WRJ VAMC.

- ***mHealth Component:***
- As described in the VA BIC manual, the intervention staff member directs patients to a wide variety of resources available within and outside the VA that may assist them in their recovery after discharge. One of these resources includes the My3App to help with suicide prevention in veterans. The app is a free app available for Android or iPhone and is owned and maintained by Vibrant Emotional Health, the administrator of the National Suicide Prevention Lifeline.

[figure not shown]
While the My3App has been endorsed by the VA, the app has not been formally tested in Veterans and is not currently incorporated in a standard fashion in discharge care practices. The intervention staff member will introduce the app as part of the brief educational intervention and will provide formal education around the role of the app in follow-up care. The interventionist will continue to encourage use of the app at each follow-up visit.

1) ***Behavioral health coach:*** The study therapist will educate patients on My3 during the brief educational visit and set up the app on the patient's phone. In this study, the study therapist will act in the role of behavioral health coach and therefore, in this role, their VA-issued iPhone number will be added to the patient's app. In their role as "Coach," the study therapist will be available to the patient between follow-up visits to answer any question and facilitate mental health treatment engagement. If My3 app were to be implemented into routine practice, the "Coach" would be a mental health provider (e.g., suicide prevention coordinator (SPC)).

2) ***Support network:*** As shown in **Figure 3**, the app includes a support network that consists of a "behavioral coach" as well as up to two additional support persons. The patient will add the VA-issued cell phone number of the interventionist as their "behavioral coach."

The patient will also select up to two support persons to add to the app. The interventionist and the patient together will decide who these individuals should be. By adding these individuals to the app, the patient will have easy access to their phone numbers, which will continue to be stored in the patient's contact list. The app will also directly input the support person's phone number into the patient's keypad, facilitating a quick and easy way to call the support person. Importantly, this information is not stored within the app itself. The patient will be encouraged to reach out to their support persons throughout the study period for positive emotional support as they continue to recover after discharge. The patient can also reach out to the "behavioral coach" for support.

**Figure 3.** How the my3 app works to support connectedness.

3) **Safety plan:** the patient will enter an abbreviated safety plan into the app, which will include strategies that they will use to support their well-being after discharge. The interventionist and patient will discuss this plan at follow-up contact visits and consider whether there is any need to further refine this plan. The patient may wish to share their safety plan with the two support persons they have chosen to be included on the app. This can be shared via email if the patient has the support person's email address in their contact list. Similarly to the call feature of the app, email addresses are not stored within the app itself. The app simply directs the patient to their main email app on their phone.

[figure not shown]
4) **Educational materials:** As shown in **Figure 3**, the patient can access educational materials related to suicide prevention on the app. These materials are standard on the app, and therefore, all patients will have access to the same material. Patients can use these interactive educational materials at any time to gain skills in supporting their mental health.

**Standard Psychiatric Hospital Discharge Care:** Patients assigned to the PEACE intervention as well as the control condition will receive the standard VA hospital discharge care that occurs as part of psychiatric hospitalization. VA current standard psychiatric hospital discharge care includes five core elements. First, patients and their outpatient providers are required to be involved in discharge planning. Second, patients should be offered evidence-based treatments to address their mental health symptoms. Third, the inpatient team should work with the patient to complete a safety plan prior to discharge. Fourth, the inpatient team should arrange two follow-up care visits within 30 days of discharge. Fifth, the inpatient team in conjunction with the SPC assess whether patients are appropriate to be placed on the High Risk for Suicide List. Patients who are placed on the High Risk for Suicide List receive enhanced oversight as outlined in VA policy. More recently, this enhanced care was renamed the Suicide Prevention Pathway. The SPC oversees the following elements of the Suicide Prevention Pathway: 1) The SPC reminds the mental health provider that the patient should be scheduled to be seen four times within the first 30 days following hospitalization; 2) The primary care or mental health provider is expected to tailor the patient's treatment to address his/her unique risk factors for suicide; 3) The SPC places a pop-up flag in the medical record to alert providers of the patient's high-risk status; and 4) The continued need for the patient to remain on the High Risk for Suicide List is reassessed by the SPC every three months. Of note, at the clinical discretion of the inpatient treatment team and the SPC, some patients may be assigned to the Suicide Prevention Pathway but may not meet criteria for the High Risk for Suicide List. Per VA policy, SPCs are not required to provide clinical care.

**Organizing framework for PEACE's Anti-Suicidal Effect:** As shown in **Figure 4** below, based on the 3ST and our pilot data, we hypothesize that PEACE will reduce the risk for suicide after psychiatric

hospitalization through the following mechanisms: First, suicide-prevention education and ongoing contact with a person at risk for suicide may help to facilitate continuity of care and reinforce the importance of engaging in treatment after discharge. MI may also promote self-efficacy and the ability to overcome barriers to treatment engagement. Because a person is receiving continuous mental health treatment after discharge, he/she may experience a lessening of symptoms of mental illness and, thus, a decrease in the psychic pain associated with mental illness. The 3ST suggests that a decrease in psychic pain and

**Figure 4. Organizing Framework for PEACE Intervention\***

\*measures described in outcomes section; pt =patient

hopelessness may decrease suicide risk. Second, PEACE may help patients to feel more socially connected. Because patients are more supported after discharge and experience increased social connectedness, this will also help to prevent their suicidal ideation from worsening. Finally, because patients are better educated about means restriction as part of the brief educational intervention, patients may take steps to mitigate their practical capacity for suicide. Together, these factors may reduce the risk for suicide after psychiatric discharge.

**Outcome Measures:** As outlined in **Table 2**, we will use several standardized instruments to collect information on primary and secondary outcomes throughout the study. Copies of assessment tools are available in the **Assessment Manual**.

**Table 2:** Overview of Standardized Assessment Measures and Timing of Assessment

Outcome	Instrument	Measurement Methods				Timing of Assessment			
		Cronbach's $\alpha$	Length	Time*	0M	1M	3M	6M	
Diagnosis	MINI	N/A	N/A	15	X	-	-	-	
Suicidal Ideation	BSS	0.87 – 0.97	21 items	10	X	X	X	X	
Hopelessness	BHS	0.87 – 0.93	20 Items	10	X	X	X	X	
Connectedness	INQ-15	0.89 – 0.91	15 items	5	X	X	X	X	
Connectedness	MSPSS	0.85 – 0.91	12 items	5	X	X	X	X	
Engagement	SRCS	0.89	17 items	5	X	X	X	X	
Suicide Attempts	C-SSRS	N/A	7 items	5-10	X	X	X	X	
App Engagement	AES	0.839	7 items	5	-	X	X	X	
Estimated time (in minutes) to complete assessments					60	50	50	50	

AES = App Engagement Scale; BHS = Beck Hopelessness Scale; BSS = Beck Scale for Suicidal Ideation; CSSR-S = Columbia Suicide Severity Rating Scale; INQ-15 = Interpersonal Needs Questionnaire-15; M = months; MINI = MINI International Neuropsychiatric Interview; MSPSS: Multidimensional Scale of Perceived Social Support; N/A = Not applicable; SRCS: The Suicide-Related Coping Scale; \*Time is described in minutes

**Baseline Characteristics:** We will collect socio-demographic data from patient report and the electronic medical record such as age, sex, marital status and service history (e.g., branch, era, combat exposure). We will also collect diagnostic information using the MINI International Neuropsychiatric Interview (MINI), which has been validated against the Structured Clinical Interview for Diagnostic and Statistical Manual of Mental Disorders (DSM). The MINI is a short, structured diagnostic interview that, on average, takes about 15 minutes to administer. We will inquire about any history of suicide attempts using the validated Columbia Suicide Severity Rating-Scale (C-SSRS). The C-SSRS includes a 7-item subscale that assesses for actual and interrupted suicide attempts.

**Primary Outcome (Suicidal Ideation):** The primary outcome will be assessed using the Beck Scale for Suicidal Ideation (BSS). Patients will be asked about their current suicidal ideation (i.e., past week) at assessments 1 as well as at assessments 2, 3, and 4. The BSS is a self-reported questionnaire that assesses severity of suicidal ideation. The BSS measures attitudes, behaviors, and plans to die by suicide. Each item on the BSS is scored on a scale from 0 to 2 and the first 19 of the 21 items are used to calculate a total score ranging from 0 – 38. The BSS has high reliability and is a valid measure of suicidal ideation. There is also evidence that the BSS is measurement invariant across time. The BSS is widely used in clinical trials, is sensitive to clinical change, and unlike most other measures of suicidal ideation, higher scores on the BSS are associated with death by suicide. While there is no established BSS cutoff score to classify suicide risk as

high, low, or none, there is evidence that higher scores on the BSS correspond to more severe suicidal ideation. There is evidence that an improvement of five points or more on the total BSS scores may be clinically relevant.

**Secondary Outcome (Patient Engagement):** We will measure patient engagement in treatment at assessment 1 as well as at assessments 2, 3 and 4. Patient engagement is a complex phenomenon to measure. The term 'patient engagement' encompasses various aspects of care related to a patient's motivation and intent to be an active participant in addressing their healthcare needs. To date, there is no agreed-upon measure in the literature that incorporates all aspects of the experience of 'patient engagement'. In the field of mental health, there is some notion that 'patient engagement' should mean that a patient experiences collaborative care, feels supported during their treatment, and adopts 'good practices' or behaviors that support their overall well-being. Therefore, only assessing whether a patient attended a mental health appointment may not adequately reflect treatment engagement. There is also evidence that symptom severity can preclude patients from engaging in care. Pfeiffer *et al.* found that, despite improvements in timely outpatient follow-up after VA psychiatric hospitalization, there were no significant changes in readmission or antidepressant treatment. In fact, Bernet *et al.* found that appointment intensity was higher in Veterans who reattempted suicide after discharge versus those who did not reattempt. Furthermore, in reviewing our data thus far from our trial on Ground East, we have identified that our current measures of engagement may not be adequately covering a key component of patient engagement as it relates to suicide including self-efficacy around managing suicide risk. This is a key concept that is part of the VA BIC intervention. Thus, we conceptualize that engagement includes patient activation, continuity of care, and self-efficacy.

- Patient activation: Patient activation is defined as "an individual's knowledge, skill and confidence for managing their health and health care." Individuals who demonstrate higher degrees of patient activation have been found to be more likely to engage in health-promoting behaviors and to experience better outcomes. Because our trial focuses specifically on activation and related self-efficacy in avoiding suicidal behavior after discharge, we will administer the validated Suicide-Related Coping Scale (SRCS). This scale includes 17 questions related to a patient's perception of their ability to cope with suicidal thoughts. Each item is assessed using a 5-point Likert scale and the measure has been developed based on two studies of suicide prevention strategies conducted within Veteran populations. The scale includes two subscales including an External Coping subscale and an Internal Coping Subscale. Both subscales have shown good acceptable internal consistency. The two factors are also sensitive to change over time. Higher scores on the scale suggest better coping.
- Continuity of care: There is some evidence that improved continuity of care may lead to better mental health outcomes. However, a single, valid, standardized measure of continuity of care for mental health has not been described in the literature. Work by Greenberg *et al.* in Veterans who were discharged from a VA inpatient mental health unit provides sufficient evidence that three aspects of continuity of care after psychiatric hospitalization (regularity of care, continuity of treatment across organizational boundaries, and intensity of treatment) are associated with improvements in overall mental health. We will use the three measures of continuity of care as validated by Greenberg *et al.* This includes:
  - a) Continuity of care: Measure of whether a patient discharged from the inpatient MH unit received any MH outpatient treatment in the first month and between 1 – 3 m after discharge.
  - b) Regularity of care: The number of months in the 3 m after the baseline assessment in which the patient attended at least 1 MH visit (Range 0 – 3 m), and
  - c) Intensity of care: Measure of the total number of MH visits between initial entry into the

study and the last study assessment.

In addition, we will also evaluate evidence of disruptions of care including no-show and cancelled appointments. We will abstract these measures from the electronic medical record. Since it is possible that some patients may receive portions of their care outside of the VA system, we will also ask patients to self-report on non-VA care.

- **Hopelessness**: To gather clinical evidence of treatment engagement, we will assess hopelessness at baseline and at follow-up assessments using the Beck Hopelessness Scale (BHS). The BHS is a 20-item self-report scale that assesses hopelessness over the past seven days. Patients comment on feelings about the future, loss of motivation, and future expectations. Total scores range from 0 to 20, with higher scores suggesting more hopelessness. Higher scores on the BHS are associated with increased suicide risk. The BHS has good reliability and validity and is sensitive to change. The psychometrics of the BHS in the Veteran population have not been studied, but the BHS has been used in other studies of the Veteran population.
- **Secondary Outcome (Connectedness)**: We defined social connectedness (or connection) as ‘the extent to which an individual is socially connected [that] takes a multifactorial approach including 1) connections to others via the existence of relationships and their roles; 2) a sense of connection that results from actual or perceived support or inclusion; and 3) the sense of connection to others that is based on positive and negative qualities’ (Holt-Lunstad et al 2017, page 521). Social connectedness is a complex construct and the literature highlights that there is no single, ideal measure that adequately captures all aspects of this construct or can be tied directly to suicide risk. In this setting, we chose Holt-Lunstad et al’s (2017) definition of social connectedness because their work is widely recognized, their framework is comprehensive, and draws upon factors that may be tied to poor outcomes including suicide. Holt-Lunstad et al 2017 (page 521) define the three domains of social connectedness as follows: 1) Structural (‘the existence and interconnections among differing social ties and roles’); 2) Functional (‘functions provided or perceived to be available by social relationships’ including ‘feelings of isolation, disconnectedness, and not belonging’); and 3) Quality (‘perceptions of positive and negative aspects of social relationship’). Within each of the aforementioned domains, there are many measures to select from and some of these measures have been studied in the context of suicide risk. We were judicious in selecting two measures that we believe will enable us to tap into the domain of interest that our intervention is designed to target (i.e. functional), while not overburdening the enrolled patients with excessive measurements. We acknowledge that there is no single comprehensive and universally accepted measure of social connectedness. We will use two scales that we believe provide synergistic information about this construct. These scales both address social connectedness and have shown association with suicidal behavior. The Interpersonal Needs Questionnaire-15 (INQ-15) taps into a major component of the functional domain of social connectedness, namely perceived inclusion. The INQ-15 is a 15-item self-report scale that measures thwarted belongingness and perceived burdensomeness. Thwarted belongingness measures an individual’s perception that their ‘fundamental need for connectedness’ is left unmet (Van Orden 2012, page 198). Each item is measured on a 7-point Likert scale, with higher scores suggesting lower perceived connectedness. The INQ-15 has good reliability and validity in the Veteran population. Higher scores on the INQ-15 have been associated with suicide risk. The Multidimensional Scale of Perceived Social Support (MSPSS) The MSPSS also taps into a major component of the functional domain of social connectedness, namely perceived social support. The MSPSS is a 12-item self-reported scale that is designed to ask about support from several sources including friends, family and significant other. The scale has been shown to have good internal and test-retest reliability as well as good validity. There is some evidence that perceived social support as measured by the MSPSS may also be associated with

suicide risk.

**Secondary Outcome (Suicide Attempts):** We will assess for non-fatal and fatal suicide attempts at one and three months after discharge using the C-SSRS. The C-SSRS is a valid and reliable scale that includes a seven-item subscale that asks patients to self-report on actual attempts, interrupted attempts, aborted attempts, and preparatory acts or behaviors. The scale asks the assessor to document the actual and potential lethality of these behaviors. The C-SSRS is widely used in the VA. The psychometrics of the C-SSRS in Veterans is unknown. We will also review suicide behavior reports (SBR) in the electronic medical record. SBRs are required in the VA and include information on suicide attempts, suicide deaths, and other types of suicidal behaviors including interrupted attempts.

[figure not shown]
**Secondary Outcome (App engagement):** Several measures have been selected to aid in a planned secondary analysis of the data to characterize the relationship between app engagement and outcomes in patients assigned to the intervention arm. Although mHealth is being used with increasing frequency to address various health behaviors, there is a dearth of evidence on effective methods to assess app engagement, though many approaches exist. Therefore, we will administer the App Engagement Scale (AES) at one-, three-, and six- months. Notably, the one- and three-month AES assessment will include the period during which the patient is receiving the PEACE intervention; however, the six-month assessment will measure whether the Veteran decided to continue to use the app on their own even after the intervention period ended and the intervention staff member was removed from the social network. The AES is adapted from the end-user version of the Mobile Application Rating Scale (uMARS). The AES has been studied in patients with mental health conditions, has been shown to have good internal reliability, and is strongly related to app engagement.

**Study Design:** As shown in Figure 5, patients allocated to the PEACE intervention will meet with the study therapist prior to discharge. During this visit, they will receive the first intervention visit. The intervention will be delivered in a private office on GE. After discharge, patients will participate in seven regular follow-up contacts with the study therapist over a period of three months in addition to use of the My3 app.

Depending on patient preference, the regular contacts will occur in a private office on the WRJ VAMC campus or the contacts will occur over the phone or VA Video Connect.

- All patients (including patients randomized to PEACE) will have access to standard discharge care. Furthermore, regardless of study assignment, all patients will undergo four outcome assessments including assessment 1 (baseline or study entry, occurs just prior to hospital discharge)(0M), assessment 2 (occurs one month after baseline assessment) (1M), assessment 3 (occurs three months after baseline

